## **2 Study Design**

## **2.1 Summary**

This is a prospective, randomized, unblinded, open-label, active controlled pilot study to evaluate the efficacy and safety of ticagrelor plus aspirin versus clopidogrel plus aspirin in patients with Rutherford Stage IV to VI PAD that have undergone a percutaneous transluminal angioplasty (PTA) of the lower extremities in the past 2 weeks.

This study will be conducted at the Cleveland Clinic and University Hospital in Cleveland, Ohio. A total of 60 patients are planned for this study.

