### **8.1 Adverse Events**

The following adverse events will be collected from the time that informed consent is obtained for this study:

- Self-reported shortness of breath
- Symptomatic bradycardia defined as self-reported symptoms of shortness of breath, chest discomfort, or dizziness with a confirmed heart rate of < 45 bpm at the time of the symptoms.
- Adverse events that are not listed in the current labeling for the drugs (see Appendix A and Investigator Brochure for ticagrelor).
- Events that lead to discontinuation of drug or result in a dose modification.

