### **8.3 Other Events of Special Interest Considered as Serious**

- Major bleeding defined as a composite of fatal bleeding, intracranial bleeding, hypovolemic shock or severe hypotension due to bleeding requiring pressors, or need for transfusion of at least 2 units in any 24-hour period.
- Major adverse limb events (surgical limb loss, major repeat revascularizations including thrombectomy, thrombolysis, or major lower extremity surgical procedure).

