### ADVERSE REACTIONS

Bleeding, including life threatening and fatal bleeding, is the most commonly reported adverse reaction. (6.1)  
To report SUSPECTED ADVERSE REACTIONS, contact Mylan Pharmaceuticals Inc. at [name] ([name]) or FDA at [name] or <http://www.fda.gov/medwatch>.

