#### Bleeding

##### CURE

In CURE, clopidogrel use with aspirin was associated with an increase in major bleeding (primarily gastrointestinal and at puncture sites) compared to placebo with aspirin (see Table 1). The incidence of intracranial hemorrhage (0.1%) and fatal bleeding (0.2%) were the same in both groups. Other bleeding events that were reported more frequently in the clopidogrel group were epistaxis, hematuria, and bruise.

The overall incidence of bleeding is described in Table 1.

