**Table 1: CURE Incidence of Bleeding Complications (% Patients)**

Event	Clopidogrel (+ aspirin)* (n = 6,259)	Placebo (+ aspirin)* (n = 6,303)
Major Bleeding†	3.7*	2.7§
Life threatening bleeding	2.2	1.8
Fatal	0.2	0.2
5 g/dL hemoglobin drop	0.9	0.9
Requiring surgical intervention	0.7	0.7
Hemorrhagic strokes	0.1	0.1
Requiring inotropes	0.5	0.5
Requiring transfusion (≥ 4 units)	1.2	1
Other major bleeding	1.6	1
Significantly disabling	0.4	0.3
Intraocular bleeding with significant loss of vision	0.05	0.03
Requiring 2 to 3 units of blood	1.3	0.9
Minor Bleeding¶	5.1	2.4

\* Other standard therapies were used as appropriate.

† Life threatening and other major bleeding.

‡ Major bleeding event rate for clopidogrel + aspirin was dose dependent on aspirin: < 100 mg = 2.6%; 100 mg to 200 mg = 3.5%; > 200 mg = 4.9% Major bleeding event rates for clopidogrel + aspirin by age were: < 65 years = 2.5%, ≥ 65 to < 75 years = 4.1%, ≥ 75 years = 5.9%

§ Major bleeding event rate for placebo + aspirin was dose dependent on aspirin: < 100 mg = 2%; 100 mg to 200 mg = 2.3%; > 200 mg = 4% Major bleeding event rates for placebo + aspirin by age were: < 65 years = 2.1%, ≥ 65 to < 75 years = 3.1%, ≥ 75 years = 3.6%

¶ Led to interruption of study medication.

Ninety-two percent (92%) of the patients in the CURE study received heparin or low molecular weight heparin (LMWH), and the rate of bleeding in these patients was similar to the overall results.

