**Table 2: Incidence of Bleeding Events in COMMIT (% Patients)**

Type of bleeding	Clopidogrel (+ aspirin) (n = 22,961)	Placebo (+ aspirin) (n = 22,891)	p-value
Major* noncerebral or cerebral bleeding†	0.6	0.5	0.59
Major noncerebral	0.4	0.3	0.48
Fatal	0.2	0.2	0.90
Hemorrhagic stroke	0.2	0.2	0.91
Fatal	0.2	0.2	0.81
Other noncerebral bleeding (non-major)	3.6	3.1	0.005
Any noncerebral bleeding	3.9	3.4	0.004

\* Major bleeds were cerebral bleeds or non-cerebral bleeds thought to have caused death or that required transfusion.

† The relative rate of major noncerebral or cerebral bleeding was independent of age. Event rates for clopidogrel + aspirin by age were: < 60 years = 0.3%, ≥ 60 to < 70 years = 0.7%, ≥ 70 years = 0.8%. Event rates for placebo + aspirin by age were: < 60 years = 0.4%, ≥ 60 to < 70 years = 0.6%, ≥ 70 years = 0.7%.

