#### COMMIT

In patients with STEMI, the safety and efficacy of clopidogrel were evaluated in the randomized, placebo-controlled, double-blind study, COMMIT. COMMIT included 45,852 patients presenting within 24 hours of the onset of the symptoms of myocardial infarction with supporting ECG abnormalities (i.e., ST-elevation, ST-depression or left bundle-branch block). Patients were randomized to receive clopidogrel (75 mg once daily) or placebo, in combination with aspirin (162 mg per day), for 28 days or until hospital discharge, whichever came first.

The primary endpoints were death from any cause and the first occurrence of re-infarction, stroke or death.

The patient population included 28% women, 58% age ≥ 60 years (26% age ≥ 70 years), 55% patients who received thrombolytics, 68% who received ACE-inhibitors, and only 3% who underwent PCI.

As shown in Table 5 and Figure 4 and Figure 5 below, clopidogrel significantly reduced the relative risk of death from any cause by 7% ( $p = 0.029$ ), and the relative risk of the combination of re-infarction, stroke or death by 9% ( $p = 0.002$ ).

Table 5: Outcome Events in the COMMIT Analysis

[figure not shown]
Event	Clopidogrel (+ aspirin) (N = 22,961)	Placebo (+ aspirin) (N = 22,891)	Odds ratio (95% CI)	p-value
Composite endpoint: Death, MI, or Stroke*	2,121 (9.2%)	2,310 (10.1%)	0.91 (0.86, 0.97)	0.002
Death	1,726 (7.5%)	1,845 (8.1%)	0.93 (0.87, 0.99)	0.029

Non-fatal MI †	270 (1.2%)	330 (1.4%)	0.81 (0.69, 0.95)	0.011
Non-fatal Stroke ‡	127 (0.6%)	142 (0.6%)	0.89 (0.70, 1.13)	0.33

[figure not shown]
\* The difference between the composite endpoint and the sum of death + non-fatal MI + non-fatal stroke indicates that nine patients (two clopidogrel and seven placebo) suffered both a non-fatal stroke and a non-fatal MI.

† Non-fatal MI and non-fatal stroke exclude patients who died (of any cause).

\* All treated patients received aspirin.

[figure not shown]
Figure 4: Cumulative Event Rates for Death in the COMMIT Study\*

\* All treated patients received aspirin.

[figure not shown]
Figure 5: Cumulative Event Rates for the Combined Endpoint Re-Infarction, Stroke or Death in the COMMIT Study\*

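### Section 8.1 gives no collection route for a labeled bleed that is non-major, non-serious and leads to no drug change, in a trial that says it evaluates the safety of two antiplatelet regimens (cheap improvement, lower priority)

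*Combined protocol and SAP*

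**What the plan says.** Section 2.1 describes a pilot study "to evaluate the efficacy and safety of ticagrelor plus aspirin versus clopidogrel plus aspirin". Section 8 defines an adverse event broadly, but Section 8.1 then lists what will be collected. The list has four items: self-reported shortness of breath; symptomatic bradycardia; "Adverse events that are not listed in the current labeling for the drugs", with a pointer to Appendix A and the ticagrelor Investigator Brochure; and events that lead to discontinuation or dose modification. The Synopsis list has the same labeling filter. Section 8.2 adds serious events. Section 8.3 adds major bleeding, whose lowest threshold is "need for transfusion of at least 2 units in any 24-hour period".

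The clopidogrel label in Appendix A states: "Bleeding, including life threatening and fatal bleeding, is the most commonly reported adverse reaction". On lesser bleeds in one of its trials it adds: "Other bleeding events that were reported more frequently in the clopidogrel group were epistaxis, hematuria, and bruise".

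Section 8.5 names three safety endpoints: major bleeding, dyspnea and symptomatic bradycardia. Section 9.1 sends safety endpoints and adverse events to Fisher's exact test. Under Section 10.2 the Medical Monitor works from the case report forms and the AE and SAE forms.

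**The concern.** For clopidogrel, the labeling filter removes milder forms of the reaction that its own label calls the most common. A nosebleed, hematuria or bruising that is not serious and leads to no change of drug would not be recorded. The bleeding comparison would then stop at events that are major, serious or drug-changing, and the Medical Monitor would not see the rest on the AE forms. Laboratory data do not fill the gap, because hemoglobin and hematocrit are recorded at screening only and the month 3 and month 6 visits list no laboratory tests.

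The filter may also act differently in the two arms. It refers to the labeling of the drugs without saying whether an event is checked against both documents or only against the one for the patient's own drug. If it is applied drug by drug and the documents differ, the same bleed could be recorded in one arm and not in the other.

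**Working it through.** **Collection routes.** The plan gives no figure to reproduce here, so the check is of the rules themselves. Take a bleed without dyspnea or bradycardia and classify it by four yes/no features: labeled, drug changed, serious, major. That gives 2^4 = 16 combinations.

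- Not labeled: collected (8.1).
- Drug discontinued or dose modified: collected (8.1).
- Serious, including hospitalization or an important medical event: collected (8.2).
- Major: collected (8.3).

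Exactly one combination has no route: labeled, no drug change, not serious, not major. The visit instruction to collect AEs and SAEs does not say that it widens the Section 8.1 list.

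**Which arms.** For clopidogrel, Appendix A shows that bleeding is labeled. For ticagrelor there are three cases.

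- The filter removes anything on either drug's list: the gap covers both arms.
- The filter is applied drug by drug and the brochure lists the bleed: the gap again covers both arms.
- The filter is applied drug by drug and the brochure does not list it: only clopidogrel bleeds are lost.

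The brochure is not in the documents, so the case cannot be settled.

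**Scale, illustrative only.** The documents give no rate for this class of bleed. The nearest is Table 2 of the label (COMMIT), in the row beginning "Other noncerebral bleeding (non-major": 3.6% with clopidogrel plus aspirin and 3.1% with placebo plus aspirin. Those were patients with myocardial infarction, treated "for 28 days or until hospital discharge, whichever came first". The row does not separate serious or drug-changing bleeds, which makes 3.6% too high for the gap. The exposure is far shorter than 6 months, which makes it too low. Half and double the rate are assumed as a range.

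Expected patients = n × p. Chance of at least one = 1 − (1 − p)^n.

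| p | Clopidogrel arm, n = 30 | Both arms, n = 60 |
|---|---|---|
| 1.8% (assumed half) | 0.5 patients; 1 − 0.982^30 = 42% | 1.1; 66% |
| 3.6% | 1.1 patients; 1 − 0.964^30 = 67% | 2.2; 1 − 0.964^60 = 89% |
| 7.2% (assumed double) | 2.2 patients; 1 − 0.928^30 = 89% | 4.3; 99% |

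The n = 30 column is what the documents support. The n = 60 column holds only if the gap covers both arms.

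**What the extra counts could show.** With 30 per arm, two-sided Fisher's test gives p = 0.052 for 5 v 0 and p = 0.024 for 6 v 0. Its exact power for 3.6% v an assumed 7.2% is 0.7%. One event in 30 has an exact 95% interval of 0.1% to 17.2%. These data can describe; they cannot separate the arms.

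**The case against.** The strongest reply is that the narrow scope was chosen. Both drugs are approved, Section 8.4 says the study is exempt from IND reporting, and the same selective list appears in the Synopsis and in Section 8.1. Neither the Synopsis objectives nor Section 3.1 states a safety objective, and each of the three declared safety endpoints has a collection route in Section 8. The extra events would be few, self-reported by unblinded patients, and recalled at two visits about three months apart.

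Most of this stands. The gap may be a deliberate pilot choice and is not a contradiction. What remains is that Section 2.1 claims to evaluate safety, that a stated rule (not mere silence) drops these bleeds, and that the rule is ambiguous between arms.

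A reader might infer more than the documents support:

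- *That all bleeding below major is lost.* It is not. Milder bleeds are collected if they are serious or change the drug.
- *That the 5.1% minor bleeding in the label's Table 1 (CURE) sizes the gap.* Its footnote defines those bleeds as ones that "Led to interruption of study medication". Section 8.1 may already collect at least some of them, although it does not say whether a temporary interruption counts.
- *That 2.2 of 60 patients is the expected loss.* That takes the ticagrelor arm as shown, which it is not.

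**Conclusion.** The point holds as a cheap improvement of lower priority. A labeled bleed that is non-major, non-serious and changes no drug is not collected. This is shown for clopidogrel and is open for ticagrelor. On an illustrative 3.6%, about 1.1 of 30 clopidogrel patients would be affected, with a 67% chance of at least one (42% to 89% over the assumed range). The primary endpoint and the declared safety endpoints are untouched.

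Two minor notes stand apart and add no weight to this conclusion.

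- The Synopsis AE list joins shortness of breath to symptomatic bradycardia, while the Synopsis safety evaluations, Section 8.1 and Section 8.5 list dyspnea separately. A reader might infer that dyspnea alone would go uncollected. Section 8.1 is clear that it is collected, so this is a wording slip.
- Exclusion 5 is defined by baseline transaminase and bilirubin, but neither appears among the 12 tests in either baseline laboratory list (the Study Visits footnote and Section 6.1). A reader might infer that the criterion cannot be applied. Section 11.1 allows medical records as a source, so it can be; the plan simply requires no such value to be recorded.

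**What to change.** In Section 8.1 and the Synopsis AE list, add: *all bleeding events, regardless of labeling, collected identically in both arms*. Classify each as major by the Section 8.3 definition or as non-major; no further severity scale is needed. In Section 9.1, state that non-major bleeding is reported by arm as n, % and 95% confidence interval, and is left out of the Fisher comparisons.

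The cost is a wording amendment and a few eCRF fields at the month 3 and month 6 visits, where AEs are already collected. The counts will rest on open-label self-report and should be read cautiously.

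In the same amendment, reconcile the Synopsis dyspnea bullet with Sections 8.1 and 8.5, and reconcile exclusion 5 with the recorded baseline laboratory tests. For the latter the cost is transcription if local results exist; the documents do not say whether they do.

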### **8.2 Serious Adverse Events**

The following SAEs will be collected from the time that informed consent is obtained until the month 6 visit:

- Death.
- Life threatening AEs.
- Requires inpatient hospitalization or prolongation of existing hospitalization.

- A disability/incapacity.
- A congenital anomaly/birth defect in the offspring of a patient who received drug.
- Important medical event that may jeopardize the subject or may require medical intervention to prevent one of the outcomes listed above.
  - Medical or scientific judgment should be exercised in deciding whether expedited reporting is appropriate in this situation. Examples of medically important events are intensive treatment in an emergency room or at home for allergic bronchospasm, blood dyscrasias, or convulsions that do not result in hospitalizations; or development of drug dependency or drug abuse.

### **8.3 Other Events of Special Interest Considered as Serious**

- Major bleeding defined as a composite of fatal bleeding, intracranial bleeding, hypovolemic shock or severe hypotension due to bleeding requiring pressors, or need for transfusion of at least 2 units in any 24-hour period.
- Major adverse limb events (surgical limb loss, major repeat revascularizations including thrombectomy, thrombolysis, or major lower extremity surgical procedure).

### **8.4 Documentation and Reporting of Adverse Events**

Prompt reporting of the SAE to the Sponsor is essential so that legal and ethical obligations can be fulfilled. SAEs will be reported to the Sponsor within 24 hours of learning of the event. The causality of the SAE (the relationship to the study treatment/procedures) will be assessed by the investigator and reported to the Sponsor. The SAE will also be documented on the appropriate eCRF.

Since the Critical Limb Ischemia Study is exempted from IND reporting, the Sponsor does not have the responsibility to report any AEs/SAEs to the FDA. The Investigator will report all SAEs (regardless of causality or expectedness) and cases of pregnancy and overdose to the Sponsor and the Sponsor will report these events to AstraZeneca, so they can fulfill the regulatory reporting requirement.

The SAE awareness date will be the date that the investigator determines that the event meets protocol-specific criteria for an SAE. The SAE will be reported to AstraZeneca by the Sponsor within 24 hours of awareness.

The investigator is responsible for informing the IRB of the SAE as per local requirements.

The Sponsor will send the SAE report that will contain the MedWatch form and accompanying cover page by way of email to AstraZeneca's designated mailbox: [[contact]](mailto:[contact]). The cover page will include the following:

- Investigator sponsored study (ISS)
- The Investigator's name and address

- The study name/title and AstraZeneca ISS reference number
- The causality of the SAE as reported by the Investigator.

If a non-serious AE becomes serious, this and other relevant follow-up information must also be provided to AstraZeneca.

## **8.5 Safety Monitoring**

Safety endpoints to be assessed include major bleeding and self-reported dyspnea and self-reported symptomatic bradycardia. Major bleeding is defined as a composite of fatal bleeding, intracranial bleeding, hypovolemic shock or severe hypotension due to bleeding requiring pressors, or need for transfusion of at least 2 units in any 24-hour period. Self-reported symptomatic bradycardia is defined as self-reported symptoms of shortness of breath, chest discomfort, or dizziness with a confirmed heart rate of < 45 bpm at the time of the symptoms.

## **9 Statistical Plan**

### **9.1 Statistical Methods**

Baseline covariates will be compared with Fisher's exact test for categorical variables and two-sample t-test for continuous variables with a normal distribution or rank sum test if non-normally distributed between treatment groups. All comparisons between treatment groups will be performed as intent-to-treat using two-tailed significance testing at a value of 0.05.

Mixed model repeated measures analysis (MMRM) will be used to conduct the between-group comparison of absolute change in TcPO2 at 3 months and 6 months follow-up, with adjustment of baseline TcPO2 level following revascularization. Estimated within-group least squares (LS) means of TcPO2 and between-group differences of LS means in TcPO2 at 3- and at 6-month follow-up time points will be obtained from the MMRM modeling.

If the TcPO2 data is not normally distributed, the same MMRM method will be performed to analyze the rank transformed TcPO2 data, however the descriptive data is presented with median (interquartile range), and the between-group differences are shown using F statistics. Meanwhile, relevant nonparametric methods will be applied as sensitivity analysis. Friedman test will be conducted to compare the TcPO2 repeated measures from baseline to 6 months follow-up between the treatment groups. A Wilcoxon signed rank test will be used to assess intragroup change in TcPO2 at 3- and at 6-month follow-up.

The percent change in TcPO2 over time and other continuous secondary endpoints will be analyzed using the same strategies. Safety endpoints, adverse events and other categorical secondary endpoints will be analyzed using Fisher's exact test. The relationships between the primary endpoint of change in TcPO2 at 6 months follow-up and the continuous secondary endpoints will be explored by regression analysis.

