### **3.2 Study Endpoints**

#### **3.2.1 Primary Endpoint**

The primary endpoint is the absolute change in TcPO2 from baseline to month 6 compared between treatment groups.

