#### **4.2 Patient Enrollment and Randomization**

Enrollment will occur when a patient signs and dates an informed consent form and provides authorization to use protected health information.

A total of 60 patients will be randomized into 2 treatment groups in a 1:1 ratio (ticagrelor to clopidogrel). Permuted block randomization will be used to allocate patients to treatment groups. Fixed block sizes will be used to allocate treatment groups, thereby ensuring that sample size in each group is similar as the study progresses. Blocked randomization lists will be computer generated and blinded to the investigators. The investigator will not know the assigned treatment for a patient until the patient is randomization. Patients will not be blinded to their treatment group.

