##### **6.4.2 Measurement of TcPO2**

Assessment of TcPO2 will be performed using the Perimed Periflux System 5000 (Perimed Inc., Ardmore, PA) equipped with laser Doppler and transcutaneous oximetry function units. Before each measurement, the device will be calibrated as per manufacturer's specifications. Patients will be asked to refrain from tobacco use or caffeine 12 hours prior to TcPO2 assessment. All measurements will be performed in the supine position. A site distant from the diseased area (right subclavicular region) will be used as a reference value (12, 18).

Skin perfusion is strongly dependent upon skin temperature. Accurate and reproducible assessment of tissue oxygenation requires measurement at maximal hyperemia. Measurement at peak blood flow provides consistency of measurements at peak cutaneous blood flow reserve. Therefore, assessment of TcPO2 requires local tissue warming around the cutaneous ulcer site to

a prespecified temperature. As part of the Perimed system, the PF 5020 Temp Unit will be used to gradually warm the perimeter of the wound at sites of measurement to a steady state of 44°C (43-45°C) as per manufacturer specifications.

In patients with Stage IV (no wound) the level of the great toe will be used as the site for measurement of TcPO2. In the event of previous amputations, the most distal aspect of the foot will be used for the measurement. In order to ensure that subsequent assessments are consistent with the index measurement, the area used will be documented in the records

From room temperature (30-34°C), thermal steady state is achieved in 3-5 minutes and is maintained during tissue assessment. All subsequent TcPO2 assessments will be made at 44°C (43-45°C) to ensure maximal hyperemia and measurement accuracy. After the site of TcPO2 adhesion is prepared, the instrument is calibrated at thermal steady state (3-5 minutes). Continuous TcPO2 monitoring then commences over 10-15 minutes until transcutaneous oxygen pressure also reaches steady state.

Follow-up TcPO2 measurements (Perimed © Periflux System 5000) will be performed at 3 and 6 months after revascularization for the purposes of this study. Repeated measures for this study at 3 and 6 months are necessary to assess the interval change of TcPO2 and to provide additional accuracy of statistical modeling of secondary efficacy endpoints.

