## **7 Pharmacologic Loading Pre-revascularization**

For patients requiring revascularization, pharmacologic loading of an ADP-receptor antagonist will have been ordered as per standard of care so as to minimize risks for post-procedural arterial thrombosis. For this study, patients will have been treated with clopidogrel up to, during, and immediately after the time of revascularization as is standard of care. After revascularization, an ADP-receptor antagonist (e.g., clopidogrel) is routinely continued for 6 months, and then discontinued. Patients will be screened and randomized for the study either in the hospital after the procedure prior to discharge or at the time of the first out-patient clinic visit following revascularization (approximately one to two weeks after the procedure). Patients will be randomized to either clopidogrel or ticagrelor. After randomization patients will receive study medication (ticagrelor) with a 90-day provision through 6 months follow-up, refilled at the 3 month clinic visit.

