### **9.2 Sample size**

The goal of this study is to compare the absolute change in TcPO2 among recently revascularized patients randomized to intervention (ticagrelor) or control (clopidogrel). With 60 patients, 30 per treatment group, this study will have 90% power at an acceptably low type I error rate (0.05) to detect a clinically significant  $8 \pm 8$  mmHg difference in TcPO2, as discussed below.

It is anticipated that most revascularized patients will have a baseline TcPO2 result of approximately 40 mmHg, whereby a 25% change would reflect a final TcPO2 result of 50 mmHg. The standard deviation (SD) for TcPO2 among such a population is estimated to be 16 mmHg based on previously published data (11,19,20). The actual change in TcPO2 that might be induced by either ticagrelor or clopidogrel is unknown. However, based on our hypothesis of improved tissue oxygen tension with ticagrelor, it is anticipated that the ticagrelor group will increase TcPO2 to a greater degree with a SD for the intergroup difference approximately 50% of the baseline SD (16 mmHg). Therefore, we have designed this study to detect an intergroup difference in TcPO2 of  $8 \pm 8$  mmHg assessed at 6 months. Even if clopidogrel induces no change in TcPO2 from baseline, an 8 mmHg increase in the ticagrelor group would represent a 20% improvement over baseline.

Given these assumptions, 26 patients per group will provide sufficient power to detect a large effect size that also reflects a clinically significant change in TcPO2 values. Adjusting for non-adherence and allowing for a 5% rate of crossover from ticagrelor to controls would require 28 patients per group. Attrition rates for this study are anticipated to be low and likely < 5%.

However, given the severity of underlying illness among a population of severely symptomatic PAD, including previously reported mortality rates of 25% at 2 years (21), it seems reasonable to assume our population will have a baseline annual mortality rate of 5-10%. Adjusting the study with 30 patients per group would allow for 7.5% attrition while maintaining power to determine the desired effect.

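### Adding baseline Rutherford group to the primary MMRM would gain some precision and conditional balance at almost no cost; the plan adjusts only for baseline TcPO2

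*Combined protocol and SAP*

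**What the plan says.** - **Endpoint (Section 3.2.1).** "The primary endpoint is the absolute change in TcPO 2 from baseline to month 6 compared between treatment groups".
- **Model (Section 9.1, repeated in the synopsis).** The between-arm comparison at 3 and 6 months uses an MMRM "with adjustment of baseline TcPO 2 level following revascularization". No other covariate is named. Baseline characteristics are to be tested for differences between arms, but nothing says what follows if a difference is found.
- **Randomization (Section 4.2).** "Permuted block randomization will be used to allocate patients to treatment groups". Block sizes are fixed and no stratification factor is named.
- **Rutherford stage (Section 6.1 and the visit table).** It is recorded at screening for every patient.
- **Measurement site (Section 6.4.2).** "In patients with Stage IV (no wound) the level of the great toe will be used as the site for measurement". In patients with an ulcer the electrode sites are on the wound perimeter. After an amputation the most distal part of the foot is used. The site is documented so that later readings match it.
- **Timing of baseline (Section 7).** Patients are screened and randomized "either in the hospital after the procedure prior to discharge or at the time of the first out-patient clinic visit following revascularization". The outpatient visit falls roughly one to two weeks after the procedure.

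**The concern.** The primary endpoint pools change at a wound margin with change at intact skin near the great toe. A margin that may heal over six months and skin with no wound could plausibly change by different amounts, even from the same starting TcPO2. Baseline TcPO2 accounts for the starting level but not for a difference in later change.

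Stage is therefore a natural prognostic factor, is known before allocation, and is used in neither the randomization nor the model. With about 30 patients per arm the stage mix can differ between arms by chance. If it does, the plan offers only an unplanned adjustment, in an open-label trial. At stake is some precision, and some protection against a visible imbalance that would otherwise be argued over after the data are seen.

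**Working it through.** **Inputs from the plan (Sections 9.1 and 9.2).** Difference 8 mmHg; SD of the difference 8 mmHg, taken as half of a cross-sectional SD of 16; two-sided 0.05; 90% power; 26 per group, raised to 28 for crossover and to 30 for 7.5% attrition.

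**Assumptions, since the documents give no value.** Share of residual variance explained by stage beyond baseline TcPO2 (R²): 5–20%. Share of patients in stage IV: 50%. Difference in 6-month change between stage groups left after baseline adjustment: 2–8 mmHg. SD of change of 16 mmHg: illustrative only.

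**1. The plan's own figure.** n per group = 2 × (1.960 + 1.282)² × (8/8)² = 21.01, so 22 by the normal approximation and 23 by the t-test. The plan states 26. With 30 per group, power is 97.2% (normal) or 96.8% (t). The 26 is matched only by adding a choice the plan does not state, such as 95% power in the normal formula, or 90% power with a rank-test efficiency of 0.864 (22/0.864 = 25.5). The mismatch is on the conservative side and does not affect this point.

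**2. Power with and without the covariate.** I use 28 per arm, because 30 × (1 − 0.075) = 27.75. Residual SD = SD × √(1 − R²), standard error = residual SD × √(2/28), and power comes from the noncentral t.

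| SD of change | R² | Residual SD | SE | Power |
|---|---|---|---|---|
| 8 | 0 | 8.00 | 2.14 | 95.7% |
| 8 | 5% | 7.80 | 2.08 | 96.5% |
| 8 | 20% | 7.16 | 1.91 | 98.4% |
| 16 | 0 | 16.00 | 4.28 | 45.1% |
| 16 | 5% | 15.59 | 4.17 | 47.0% |
| 16 | 20% | 14.31 | 3.82 | 53.8% |

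If stage explains nothing, the lost degree of freedom costs less than 0.1 point of power.

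**3. Chance imbalance in stage.** Treating the arms as independent draws of 30, the SD of the arm difference in stage share is √(2 × 0.5 × 0.5/30) = 0.129. At a 30% or 70% share it is 0.118. A one-SD imbalance shifts the unadjusted estimate by 0.129 × 2 = 0.26 to 0.129 × 8 = 1.03 mmHg. At the edge of the 95% range (1.96 × 0.129 = 0.25) the shift is 0.5 to 2.0 mmHg. The design standard error is 8 × √(2/30) = 2.07 mmHg.

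**4. These are one effect, not two.** With a 50:50 split, a stage difference e explains R² = e² × 0.25/SD². At SD 8, e of 2–8 mmHg gives R² of 1.6–25%, and R² of 5–20% corresponds to e of 3.6–7.2 mmHg. At SD 16, R² of 5–20% would need e of 7.2–14.3 mmHg, mostly above the range in step 3, so the gain shown there is on the generous side. The shift and the power gain describe the same quantity and must not be added.

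**The case against.** The strongest reply is that there is no error here. A baseline-adjusted MMRM on randomized arms is unbiased over the randomization and keeps its nominal type I error; chance imbalance in stage is already covered by the standard error. Baseline TcPO2 is read after the procedure at the same documented site as the follow-up readings, so whatever stage and timing do through the starting level is already removed. Only an effect on later change remains, and the documents do not quantify it. At the plan's own SD, power is already above 95%. All of this stands, and it limits the point to an efficiency gain.

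A reader might infer more than the documents support:

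- **That the treatment estimate is biased.** It is not. An imbalance shifts the estimate in a given realized allocation, but not on average over allocations.
- **That the trial gives up substantial power.** That needs an SD of change well above 8 mmHg. Section 9.2 plans on 8, and no other SD of change appears.
- **That time since the procedure is a recorded covariate wrongly left out.** The interval can be derived, since eligibility requires an intervention in the past two weeks and Section 11.1 relies on the procedure date. But Section 6.4.1 lists the treated segment and anatomy, not the date or interval. A linear effect of days has no support in the documents either.
- **That stage is the same as measurement site.** It is not, because the amputation rule in Section 6.4.2 also moves the site.

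It is also fair to say that a stage main effect leaves the treatment effect pooled across the two kinds of site; it does not estimate separate effects. Section 3.2.2 plans a subgroup analysis in patients with non-gangrenous wounds, but that does not change the primary model.

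What the reply does not answer is why a factor known before allocation, and tied so closely to how the endpoint is measured, should be left out when including it costs so little.

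**Conclusion.** The point holds as a low-cost improvement. The primary analysis is valid without it. At the planned SD of 8 mmHg the gain is about 1 to 3 points of power; at an SD of 16 it would be about 2 to 9 points, from a base of 45%. A typical chance imbalance in stage would move the estimate by about 0.3–1.0 mmHg, less than half of one standard error. These sizes rest on assumed values for the variance explained, the stage split and the residual stage effect. If the residual stage effect is nil, the gain is nil and the loss is under 0.1 point of power. The case for stage does not depend on the timing covariate, which is optional.

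**What to change.** In Section 9.1 and in the statistical methodology part of the synopsis, prespecify baseline Rutherford group (IV vs V–VI) as a fixed covariate in the primary MMRM, alongside baseline TcPO2. Keep the baseline-only model as a named sensitivity analysis.

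Optionally, add days from the procedure to baseline TcPO2 as a further covariate. In that case the procedure date should be an explicit field on the case report form.

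For stage alone the cost is one sentence and one degree of freedom, with no new visit, measurement or data item. The optional timing term adds one more degree of freedom and the date field.
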